3.1 Inclusion criteria

Patients must meet the following criteria in order to be included in the study:

1. Has read and understands the informed consent form (ICF) and has given written IC prior to any study procedures.
2. Male or female patient ≥ 18 years of age.
3. Patient must have received previous chemotherapy for recurrent or metastatic disease. Patients may have received previous treatment with immunotherapy but this would not be considered an additional line of treatment as long as it was given without a cytotoxic agent.
4. Measurable disease is required for Part B expansion cohorts according to RECIST v1.1 criteria.

5. Radiation therapy must be completed at least 7 days prior to start of study treatment and patients must have recovered from any acute adverse effects prior to start of study treatment.
6. Eastern Cooperative Oncology Group (ECOG) Performance Status (PS) score of 0-1.
7. Baseline (within 14 days of study drug administration) laboratory values as follows:
 - Absolute neutrophil count (ANC) $\geq 1500/\mu\text{L}$
 - Haemoglobin (Hgb) ≥ 9 g/dL
 - Platelets $\geq 100,000/\mu\text{L}$
 - Alanine aminotransferase (ALT) and aspartate aminotransferase (AST) ≤ 3 x upper limit of normal (ULN) or ≤ 5 x ULN if known hepatic metastases.
 - Serum bilirubin within normal limits (WNL) or ≤ 1.5 x the ULN in patients with liver metastases; or total bilirubin ≤ 3.0 x ULN with direct bilirubin WNL in patients with well documented Gilbert's Syndrome.
 - Serum creatinine ≤ 1.5 x the ULN or a calculated creatinine clearance (CrCl) ≥ 45 mL/min measured by the Cockcroft-Gault method or 24-hour urine CrCl:
$$\text{Estimated CrCl (glomerular filtration rate [GFR])} = \frac{(140 - \text{age}[\text{years}]) \times (\text{weight} [\text{kg}]) \times F^a}{(72 \times \text{serum creatinine mg/dL})}$$

^a where F = 0.85 for females and F = 1 for males
8. Female patients who are not of childbearing potential and fertile females of childbearing potential must agree to use adequate contraceptive measures (see [Appendix F](#) for definition) from 2 weeks prior to the study and until 1 month after study treatment discontinuation, who are not breastfeeding, and who have a negative serum or urine pregnancy test within 3 days prior to start of study treatment.
9. Male patients should be willing to abstain or use barrier contraception (i.e., condoms) for the duration of the study drug exposure and for 3 months after treatment discontinuation.

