This Appendix describes the process to be followed in order to identify and appropriately report cases of Hy's Law. It is not intended to be a comprehensive guide to the management of elevated liver biochemistries. Specific guidance on the managing liver abnormalities can be found in Section 6.4.6 of the protocol.

During the course of the study the Investigator will remain vigilant for increases in liver biochemistry. The investigator is responsible for determining whether a patient meets potential Hy's Law (PHL) criteria at any point during the study.

The Investigator participates, together with AstraZeneca clinical project representatives, in review and assessment of cases meeting PHL criteria to agree whether Hy's Law (HL) criteria are met. HL criteria are met if there is no alternative explanation for the elevations in liver biochemistry other than Drug Induced Liver Injury (DILI) caused by the Investigational Medicinal Product (IMP).

The Investigator is responsible for recording data pertaining to PHL/HL cases and for reporting Adverse Events (AE) and Serious Adverse Events (SAE) according to the outcome of the review and assessment in line with standard safety reporting processes.

Definitions

Potential Hy's Law (PHL)

Aspartate Aminotransferase (AST) or Alanine Aminotransferase (ALT) $\geq 3x$ Upper Limit of Normal (ULN) **together with** Total Bilirubin (TBL) $\geq 2x$ ULN at any point during the study following the start of study medication irrespective of an increase in Alkaline Phosphatase (ALP).

Hy's Law (HL)

AST or ALT $\geq 3x$ ULN **together with** TBL $\geq 2x$ ULN, where no other reason, other than the IMP, can be found to explain the combination of increases, eg, elevated ALP indicating cholestasis, viral hepatitis, another drug.

For PHL and HL the elevation in transaminases must precede or be coincident with (i.e. on the same day) the elevation in TBL, but there is no specified timeframe within which the elevations in transaminases and TBL must occur.

Identification of Potential Hy's Law Cases

In order to identify cases of PHL it is important to perform a comprehensive review of laboratory data for any patient who meets any of the following identification criteria in isolation or in combination:

- ALT \geq 3xULN
- AST \geq 3xULN
- TBL \geq 2xULN

The Investigator will without delay review each new laboratory report and if the identification criteria are met will:

- Notify the AstraZeneca representative

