- Determine whether the patient meets PHL criteria (see [Definitions](#) within this Appendix for definition) by reviewing laboratory reports from all previous visits
- Promptly enter the laboratory data into the laboratory CRF

Follow-up

Potential Hy's Law Criteria not met

If the patient does not meet PHL criteria the Investigator will:

- Perform follow-up on subsequent laboratory results according to the guidance provided in the Clinical Study Protocol (CSP).

Potential Hy's Law Criteria met

If the patient does meet PHL criteria the Investigator will:

- Notify the AZ representative who will then inform the central Study Team

The Study Physician (SP) contacts the Investigator, to provide guidance, discuss and agree an approach for the study subject's follow-up and the continuous review of data. Subsequent to this contact, the investigator will:

- Monitor the patient until liver biochemistry parameters and appropriate clinical symptoms and signs return to normal or baseline levels, or as long as medically indicated
- Investigate the etiology of the event and perform diagnostic investigations as discussed with the Study Physician.
- Complete the three Liver CRF Modules as information becomes available
- If at any time (in consultation with the Study Physician) the PHL case meets serious criteria, report it as an SAE using standard reporting procedures

Review and Assessment Review of Potential Hy's Law Cases

The instructions in this Section should be followed for all cases where PHL criteria are met.

No later than 3 weeks after the biochemistry abnormality was initially detected, the Study Physician contacts the Investigator in order to review available data and agree on whether there is an alternative explanation for meeting PHL criteria other than DILI caused by the IMP. The AstraZeneca Medical Science Director and Global Safety Physician will also be involved in this review together with other subject matter experts as appropriate.

According to the outcome of the review and assessment, the Investigator will follow the instructions below.

If there is an agreed alternative explanation for the ALT or AST and TBL elevations, a determination of whether the alternative explanation is an AE will be made and subsequently whether the AE meets the criteria for a SAE:

- If the alternative explanation is **not** an AE, record the alternative explanation on the appropriate CRF

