- If the alternative explanation is an AE/SAE, record the AE /SAE in the CRF accordingly and follow the AZ standard processes

If it is agreed that there is **no** explanation that would explain the ALT or AST and TBL elevations other than the IMP:

- Report an SAE (report term 'Hy's Law') according to AstraZeneca standard processes.
 - The 'Medically Important' serious criterion should be used if no other serious criteria apply
 - As there is no alternative explanation for the HL case, a causality assessment of 'related' should be assigned.

If, there is an unavoidable delay, of over 3 weeks, in obtaining the information necessary to assess whether or not the case meets the criteria for HL, then it is assumed that there is no alternative explanation until such time as an informed decision can be made:

- Report an SAE (report term 'Potential Hy's Law') applying serious criteria and causality assessment as per above
- Continue follow-up and review according to agreed plan. Once the necessary supplementary information is obtained, repeat the review and assessment to determine whether HL criteria are met. Update the SAE report according to the outcome of the review.

Actions Required for Repeat Episodes of Potential Hy's Law

This section is applicable when a patient meets PHL criteria on study treatment and has already met PHL criteria at a previous on study treatment visit.

The requirement to conduct follow-up, review and assessment of a repeat occurrence(s) of PHL is based on the nature of the alternative cause identified for the previous occurrence.

The investigator should determine the cause for the previous occurrence of PHL criteria being met and answer the following question:

- Was the alternative cause for the previous occurrence of PHL criteria being met found to be the disease under study e.g. chronic or progressing malignant disease, severe infection or liver disease?

If No: follow the process described in [Potential Hy's Law Criteria met](#) of this Appendix.

If Yes:

Determine if there has been a significant change in the patient's condition[#] compared with when PHL criteria were previously met

- If there is no significant change no action is required
- If there is a significant change follow the process described in [Potential Hy's Law Criteria not met](#) of this Appendix

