[#] A 'significant' change in the patient's condition refers to a clinically relevant change in any of the individual liver biochemistry parameters (ALT, AST or total bilirubin) in isolation or in combination, or a clinically relevant change in associated symptoms. The determination of whether there has been a significant change will be at the discretion of the Investigator; this may be in consultation with the Study Physician if there is any uncertainty.

References

FDA Guidance for Industry (issued July 2009) 'Drug-induced liver injury: Premarketing clinical evaluation':

<http://www.fda.gov/downloads/Drugs/GuidanceComplianceRegulatoryInformation/Guidances/UCM174090.pdf>

Appendix D Guidelines for Evaluation of Objective Tumour Response Using RECIST 1.1 Criteria (Response Evaluation Criteria in Solid Tumours)

INTRODUCTION

This appendix details the implementation of RECIST 1.1 Guidelines ([Eisenhauer et al 2009](#)) for the D6015C00001 study with regards to Investigator assessment of tumour burden including protocol-specific requirements for this study.

DEFINITION OF MEASURABLE, NON-MEASURABLE, TARGET AND NON-TARGET LESIONS

Only patients with measurable disease at baseline should be included in the study. Measurable disease is defined by the presence of at least one measurable lesion which has not been previously irradiated.

Measurable:

A lesion, not previously irradiated, that can be accurately measured at baseline as ≥ 10 mm in the longest diameter (except lymph nodes which must have short axis ≥ 15 mm) with computed tomography (CT) or magnetic resonance imaging (MRI) and which is suitable for accurate repeated measurements.

Non-measurable:

- All other lesions, including small lesions (longest diameter <10 mm or pathological lymph nodes with ≥ 10 to <15 mm short axis at baseline*).
- Truly non-measurable lesions include the following: bone lesions, leptomeningeal disease, ascites, pleural / pericardial effusion, inflammatory breast disease, lymphangitic involvement of skin or lung, and abdominal masses/abdominal organomegaly identified by physical examination that is not measurable by CT or MRI.
- Previously irradiated lesions**
- Skin lesions assessed by clinical examination***
- Brain metastasis***

*Nodes with <10 mm short axis are considered non-pathological and should not be recorded or followed as NTL.

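### Appendix C sends a changed repeat case that meets potential Hy's Law criteria to the process for patients who do not meet them

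*Protocol*

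**What the plan says.** Protocol Appendix C defines PHL as AST or ALT at or above 3x ULN together with total bilirubin (TBL) at or above 2x ULN after the start of study medication. It sets out two processes.

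- *Potential Hy's Law Criteria not met* is for a patient who does not meet PHL. Its single instruction is: "Perform follow-up on subsequent laboratory results according to the guidance provided in the Clinical Study Protocol".
- *Potential Hy's Law Criteria met* has the sponsor's representative inform the central study team and the Study Physician contact the investigator. The patient is monitored, the aetiology is investigated and three liver CRF modules are completed. Joint review follows no later than 3 weeks after the abnormality was first detected, and on its scope the appendix says: "The instructions in this Section should be followed for all cases where PHL criteria are met".

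The section on repeat episodes states its own scope: "This section is applicable when a patient meets PHL criteria on study treatment and has already met PHL criteria" at an earlier on-treatment visit. It then asks whether the earlier episode was attributed to the disease under study. If not, the case goes to the criteria-met process. If so, there are two outcomes. The first is "If there is no significant change no action is required". The second is "If there is a significant change follow the process described in" the criteria-not-met section. A footnote explains that a significant change "refers to a clinically relevant change in any of the individual liver biochemistry parameters", or in associated symptoms. The investigator judges this and may consult the Study Physician.

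**The concern.** The significant-change branch names a process whose entry condition is false for every patient sent to it. The section is reached only by meeting PHL, and its destination is reserved for patients who do not.

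The practical effect is that an earlier attribution to disease is carried forward without re-examination, just when the picture has changed. Section 1.3.2 lists transaminase elevation as a potential risk of AZD1775. The branch can plausibly be reached in this population: inclusion criterion 7 admits patients with hepatic metastases and ALT/AST up to 5x ULN, and the appendix gives progressing malignant disease, severe infection and liver disease as examples of the qualifying earlier cause. A drug-induced injury that follows a disease-related episode could be handled as routine laboratory follow-up.

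**Working it through.** No figure in the protocol needs reproducing here. The check is to trace the decision rules.

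**1. The three branches open to a repeat PHL case**

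- Earlier cause not the disease: criteria-met process, with joint review.
- Earlier cause the disease, no significant change: no action.
- Earlier cause the disease, significant change: criteria-not-met process.

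**2. Entry conditions set side by side**

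- Repeat-episode section: the patient meets PHL now and met it before.
- Criteria-not-met process: the patient does not meet PHL.

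The two conditions exclude each other, so the third branch cannot be followed consistently.

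**3. What the destination provides**

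The criteria-not-met process defers to guidance elsewhere in the protocol. The introduction to Appendix C says that guidance on managing liver abnormalities is in Section 6.4.6. Section 6.4.6 refers increases in liver biochemistry back to Appendix C. The trail is circular and leads to no causality review.

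**4. What is lost against the criteria-met process**

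The losses are the Study Physician's guidance, the aetiology work-up, the three liver CRF modules, the joint review within 3 weeks, and the SAE route that follows from that review. The review also has a protective default. If the information needed is delayed beyond 3 weeks, the case is assumed to have no alternative explanation and is reported as an SAE. In the misrouted branch the earlier disease attribution stands instead.

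**5. Illustration (assumed values, not trial data)**

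First episode: ALT 4x and TBL 2.2x ULN, attributed to disease. Repeat: ALT 12x and TBL 5x ULN.

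- Against the PHL limits: 12/3 = 4.0 times for ALT and 5/2 = 2.5 times for TBL.
- Against the first episode: 12/4 = 3.0-fold for ALT and 5/2.2 = 2.27, about 2.3-fold, for TBL.

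If the investigator judges this a significant change, the text handles it as a case in which PHL is not met.

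**6. What still operates**

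- Appendix C: any one of ALT at or above 3x, AST at or above 3x or TBL at or above 2x triggers laboratory review and notification of the sponsor's representative.
- Section 6.8.2: holds and reductions are allowed as clinically indicated.
- Section 6.4.7: combined elevations may need to be reported as SAEs.
- Section 8.3.3: laboratory data are evaluated for potential drug-induced liver injury.

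None of these supplies the joint, timed causality review.

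**The case against.** The best defence is that the repeat-episode section is a deliberate exception. It says that handling of a repeat depends on the cause found for the earlier occurrence, so the general statement that all PHL cases are reviewed need not govern it. That stands as far as it goes. It justifies taking no action when a case attributed to disease is unchanged. It does not justify treating a changed, PHL-positive case as PHL-negative. The footnote defining a significant change would also have little purpose if a positive answer led only to laboratory follow-up.

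A second defence is that the other safeguards are enough. They are real. Section 6.4.6 excludes from AE/SAE reporting only deterioration unequivocally due to progression, and a sharp rise of unsettled cause is not that. Clinically indicated holds carry no attribution condition. However, the Grade 3/4 dose rule in Section 6.8.2 covers toxicity not attributable to the disease, and that attribution is what the joint review would settle. The safeguards reduce the harm without replacing the review.

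Two stronger readings are tempting, and the protocol supports neither.

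- *Both disease-attributed branches are defective.* The no-change branch is a deliberate rule under the section's own scoping sentence. Only one of the three branches is wrong.
- *The order rule excludes patients with Gilbert's syndrome.* Appendix C says "For PHL and HL the elevation in transaminases must precede or be coincident with (i.e. on the same day) the elevation in TBL", and criterion 7 admits "total bilirubin ≤ 3.0 x ULN with direct bilirubin WNL in patients with well documented" Gilbert's syndrome. A reader might infer that a TBL already at or above 2x ULN before dosing bars the patient from PHL. The text does not say how such an elevation is dated, but this is an ambiguity and not an error. If the elevations are dated at the visit where both limits are met, they coincide and the case qualifies. Sections 5.2.1, 6.4.6 and 6.4.7 name the same two thresholds with no order condition. Switching the rule off could also make a patient with Gilbert's syndrome and hepatic metastases PHL with no change at all, because entry allows TBL up to 3.0x and ALT/AST up to 5x ULN.

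**Conclusion.** The significant-change branch is wrong as written. One of the three repeat-episode branches sends PHL-positive patients to a process defined for PHL-negative patients, and following it literally omits the causality review.

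The conclusion rests on the wording of Appendix C alone and does not depend on baseline values or on the illustration above. How many patients would reach this branch is not in the protocol. It requires two PHL episodes, an earlier attribution to disease and a judged change, so the number is probably small. The consequence is for individual patient safety and case reporting. Sample size, endpoints and efficacy analyses are unaffected.

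**What to change.** In Appendix C, repeat episodes, change the destination of the significant-change branch from *Potential Hy's Law Criteria not met* to *Potential Hy's Law Criteria met*. This deletes one word, and any document link should be redirected to match. Leave the no-change branch and the order rule in the Definitions unchanged.

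The cost is a few more cases in joint review. The footnote gives no direction of change, so these could include patients who have improved but still meet PHL. No additional scheduled sampling is needed, because ALT, AST and total bilirubin are already collected.

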Appendix E Stages of Heart Failure – New York Heart Association Classification

The Stages of Heart Failure – New York Heart Association Classification

Class I (Mild)

No Limitation of physical activity. Ordinary physical activity does not cause undue fatigue, palpitation, or dyspnoea (shortness of breath).

Class II (Mild)

Slight limitation of physical activity. Comfortable at rest, but ordinary physical activity results in fatigue, palpitation, or dyspnoea.

Class III (Moderate)

Marked limitation of physical activity. Comfortable at rest, but less than ordinary physical activity results in fatigue, palpitation, or dyspnoea.

Class IV (Severe)

Unable to carry out any physical activity without discomfort. Symptoms of cardiac insufficiency at rest. If any physical activity is undertaken, physical discomfort is increased.

Reference

The Criteria Committee of the New York Heart Association. Nomenclature and criteria for diagnosis of diseases of the heart and great vessels. 9th ed. Boston (MA): Little, Brown & Co; 1994:253-256.

Appendix F Definition of Women of Childbearing Potential

Women of Child Bearing Potential (WoCBP) - Women between menarche and menopause who have not been permanently or surgically sterilized and are capable of procreation.

Women NOT of Childbearing Potential - Women who are permanently or surgically sterilized or postmenopausal (definitions below):

Permanent sterilisation includes hysterectomy and/or bilateral oophorectomy and/or bilateral salpingectomy but excludes bilateral tubal occlusion. Tubal occlusion is considered a highly effective method of birth control but does not absolutely exclude possibility of pregnancy. (The term occlusion refers to both occluding and ligating techniques that do not physically remove the oviducts).

- Women who have undergone tubal occlusion should be managed on trials as if they are of WoCBP (e.g. undergo pregnancy testing etc. as required by the study protocol).
- Women will be considered postmenopausal if they are amenorrhoeic for 12 months without an alternative medical cause. The following age-specific requirements apply:
- Women under 50 years old will be considered postmenopausal if they have been amenorrhoeic for 12 months or more following cessation of exogenous hormonal treatments and with LH and FSH levels in the post-menopausal range.
- Women over 50 years of age will be considered postmenopausal if they have been amenorrhoeic for 12 months or more following cessation of all exogenous hormonal treatments.

ACCEPTABLE CONTRACEPTION METHODS

Highly effective method of birth control is defined in Note 3 in ICH Guidance M3 (Nonclinical Safety Studies for the conduct of Human Clinical trials for Pharmaceuticals) as one that results in a low failure rate (e.g. less than 1 percent per year) when used consistently and correctly.

The following methods of highly effective contraception are considered acceptable by

Note that women should have been stable on their chosen method of birth control for a minimum of 2 weeks before entering the trial. Generic names and examples of trade names are given. As trade names may vary, investigators should check the generic name of any contraception to ensure suitability.

Acceptable contraception methods are:

- Total sexual abstinence (abstinence must be for the total duration of the trial and the follow-up period)
- Vasectomised sexual partner plus male condom (with participant assurance that partner received post-vasectomy confirmation of azoospermia)
- Tubal occlusion plus male condom
- Intra-uterine Device (IUD) - provided coils are copper-banded, plus male condom
- Intra-uterine system (IUS) Levonorgestrel Intra Uterine System (e.g. Mirena), plus male condom
- Medroxyprogesterone injections (Depo-Provera) plus male condom
- Etonogestrel implants (eg, Implanon, Norplan) plus male condom
- Normal and low dose combined oral contraceptive pills, plus male condom
- Norelgestromin / ethinylestradiol transdermal system plus male condom
- Intravaginal device (eg ethinylestradiol and etonogestrel) plus male condom
- Cerazette (desogestrel) plus male condom. Cerazette is currently the only highly efficacious progesterone based pill

UNACCEPTABLE CONTRACEPTION METHODS

The following methods are considered not to be highly effective and are therefore not acceptable contraceptive methods in AstraZeneca clinical trials:

- Triphasic combined oral contraceptives (COCs)
- All progesterone only pills, except Cerazette
- All barrier methods, if intended to be used alone
- Non-copper containing Intra-Uterine Devices (IUDs)
- Fertility awareness methods
- Coitus interruptus

